16. Received an agent known to be a sensitive CYP2D6 substrate or a CYP2D6 substrate with a narrow therapeutic range, a strong or moderate CYP2D6 inhibitor, or a BCRP inhibitor within 7 days or a period corresponding to 4-5 half-lives of the agent, prior to the first dose of study drug.
17. Cardiac dysfunction defined as myocardial infarction within 6 months of study entry, New York Heart Association (NYHA) Class III or IV heart failure, uncontrolled dysrhythmias or poorly controlled angina.
18. Are receiving any active treatment for thrombosis.
19. History of serious ventricular arrhythmia (e.g. VT or VF,  $\geq 3$  beats in a row), or QT interval corrected for heart rate (QTc)  $\geq 480$  ms.  
*Note: QTc values up to 500 ms will be acceptable where patient's medical history e.g. bundle branch block, is known to cause mild QTc prolongation and the condition is well controlled.*
20. Any disease, syndrome or condition which may affect significantly drug intake via oral route.
21. Any other prior or current medical condition, intercurrent illness, surgical history, physical or 12-lead electrocardiogram (ECG) findings, laboratory abnormalities, or extenuating circumstance (e.g. alcohol or drug addiction) that, in the investigator's opinion, could jeopardize patient safety or interfere with the objectives of the study.

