#### Screening (up to a maximum of 28 days prior to first dose of SEL24/MEN1703)

- ~ Demographics
- ~ Medical history
- ~ Inclusion/exclusion check
- ~ FSH/Pregnancy testing (as appropriate; pregnancy test to be conducted within 7 days of the first SEL24/MEN1703 administration)
- ~ ECOG PS

- ~ Vital signs
- ~ Physical examination
- ~ Clinical chemistry
- ~ Hematology
- ~ Coagulation
- ~ Lipid profile
- ~ Peripheral blasts
- ~ Urinalysis
- ~ ECG
- ~ Echocardiogram (or MUGA scan, if this is preferred standard, local cardiac assessment)
- ~ Bone marrow aspirate/biopsy (local bone marrow differential to be performed)
- ~ Genetic profile of AML cells (bone marrow)  
Note: An aliquot of bone marrow aspirates/biopsy will be used
- ~ PD biomarkers (blood)
- ~ CYP2D6 phenotyping (blood)
- ~ CD25 expression (blood)  
Note: An aliquot of blood taken for PD biomarker will be used
- ~ Mutational status
- ~ AML Karyotypic analysis
- ~ Transfusion status
- ~ Concomitant medication

#### Cycle 1, Day 1

- ~ Vital signs
- ~ FSH/Pregnancy testing
- ~ Physical examination
- ~ Clinical chemistry
- ~ Hematology
- ~ Coagulation
- ~ Lipid profile
- ~ Peripheral blasts
- ~ Urinalysis
- ~ ECG (pre-dose and 4-6 h post dose)
- ~ PD biomarkers (blood; pre-dose, 2-6h post dose)
- ~ Adverse events
- ~ Transfusion status
- ~ Concomitant medication
- ~ PK profile sampling (blood; pre-dose, 0.5, 1, 2, 4, 6, 8, 10-14 h post dose)
- ~ PK (urine; Part 1 only)

#### Cycle 1, Day 2

- ~ Clinical chemistry
- ~ Hematology

- ~ Coagulation
- ~ Adverse events
- ~ Transfusion status
- ~ Concomitant medication
- ~ PK sampling (blood; 24 h post C1 D1 dose/C1 D2 pre-dose)
- ~ PK (urine; collect to immediately before D2 dose, Part 1 only)

#### Cycle 1, Days 3 and 4

- ~ Clinical chemistry
- ~ Hematology
- ~ Coagulation
- ~ Adverse events
- ~ Transfusion status
- ~ Concomitant medication

#### Cycle 1, Day 7

- ~ Clinical chemistry
- ~ Hematology
- ~ Coagulation
- ~ ECG
- ~ Adverse events
- ~ Transfusion status
- ~ Concomitant medication
- ~ PK sampling (blood; 4 h and 8 h post dose)

#### Cycle 1, Day 14

- ~ Clinical chemistry
- ~ Hematology
- ~ Coagulation
- ~ Lipid profile
- ~ Peripheral blasts
- ~ PD biomarkers (blood; 2-6h post dose)
- ~ Adverse events
- ~ Transfusion status
- ~ Concomitant medication
- ~ PK profile sampling (blood; pre-dose, 0.5, 1, 2, 4, 6, 8, 10-14 h post dose)

Note: PD and PK sampling times are relative to last dose in C1.

#### Cycle 1, Day 15

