### 5.3.8. Electrocardiograms

A resting 12-lead ECG will be performed at the times given in the Schedule of Study Assessment (Table 5).

All 12-lead ECGs should be recorded while the patient is in the supine position. ECGs will be recorded at 25 mm/sec. All efforts should be made to ensure that an identical ECG machine is used to collect traces for individual patients. The Investigator or designated physician will review the ECG results.

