5.3. Study flow chart

Cycle	Screening ≤28-days	Cycle 1							Cycle 2			Cycle 3 onwards		Final Study Visit ¹⁷	Follow Up ¹⁸
		D1	D2	D3&4	D7 (±1)	D14 (±1)	D15	D17	D19	D1 (±2)	D7 (±1)	D14 (±1)	D1 (±2)	D14 (±1)	
Visit															
Demographics	X														
Medical history	X														
Inclusion/exclusion checks	X														
FSH and/or Pregnancy test ¹	X	X								X			X		X
ECOG PS	X									X			X		X
Vital signs ²	X	X								X			X		X
Physical examination ³	X	X								X			X		X
Clinical chemistry ⁴	X	X	X	X	X	X				X	X	X	X	X	X
Hematology ⁴	X	X	X	X	X	X				X	X	X	X	X	X
Coagulation ⁴	X	X	X	X	X	X				X	X	X	X		X
Lipid profile ⁴	X	X				X				X		X	X		X
Peripheral blasts ⁵	X	X				X						X		X	X
Urinalysis	X	X								X			X		X
Electrocardiogram ⁶	X	X			X					X			X		X
Echocardiogram (or MUGA scan)	X														
Bone marrow aspirate/biopsy ⁷	X												(X) [§]		(X)
Disease evaluation ⁸													(X) [§]		(X)
The genetic profile of AML cells ⁹	X												(X) [§]		(X)
PD biomarker blood sampling ¹⁰	X	X				X				X		X	X [§]	X [§]	
CYP2D6 phenotyping ¹¹	X														
CD25 Expression ¹²	X														
Mutational Status ¹³	X														
AML Karyotypic analysis	X														
Adverse events		X	X	X	X	X				X	X	X	X	X	X
Concomitant medication	X	X	X	X	X	X				X	X	X	X	X	X
Transfusion status	X	X	X	X	X	X				X	X	X	X	X	X
SEL24/MEN1703 administration ¹⁴		X - once daily dosing for 14 consecutive days in 21-day cycles													
PK sampling (blood) ¹⁵		X	X		X	X	X	X	X	X	X	X	X	X	
PK (urine collection) ¹⁶		X	X												
Follow-up assessments															X

General instructions:

- Informed Consent must be obtained using the current version of the PIS/ICF prior to commencing Screening.
- On dosing days, assessments should be performed prior to SEL24/MEN1703 dosing unless specified otherwise; tolerance windows for specific assessments are described below.
- (X) denotes an optional sample; please refer to Footnotes.
- X[§] denotes a sample not taken at every cycle; please refer to Footnotes.
- Additional assessments may be performed as clinically indicated.

Footnotes:

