- A pregnancy test is required within 7 days prior to receiving study drug. Pregnancy test may be alternatively carried out at C1D1 visit prior to first SEL24/MEN1703 administration; results of the test should be available prior to receiving study drug. Additionally, a pregnancy test is required on the first day of each study cycle and at the Final Study Visit. If the Final Study Visit is performed before 30 days has elapsed from the last study drug administration, the pregnancy test shall be postponed when 30 days (+7 d tolerance) from the last study drug intake is elapsed (i.e. when no relevant drug systemic exposure is expected). A negative pregnancy test may

be confirmed by urine or blood test. Where a urine test is positive or equivocal, a blood test must be performed to confirm the result. Patients requiring confirmation of post-menopausal status will have FSH levels assessed at Screening.

2. Vital signs include temperature, systolic blood pressure, diastolic blood pressure, heart rate and respiratory rate.
3. Physical examination includes height and weight at Screening and only weight at the start of each cycle. After Screening, further assessments may be symptom-directed.
4. For complete list of Clinical chemistry, Hematology, Coagulation, and Lipid profile parameters please refer to Appendix E of the protocol. Coagulation parameters may be assessed from the Hematology sample. Should a patient develop coagulation abnormalities at any point during the study, a comprehensive evaluation of coagulation abnormalities will be performed immediately which may include, but not be limited to repeat PT/INR, APTT, fibrinogen, D-dimer, plus a peripheral blood smear, thrombin time, to be evaluated by the Investigator in conjunction with the patient's medical history, a physical examination and concomitant medication review. Repeat testing may be performed as clinically indicated, which may include additional parameters or time-points (please also refer to Appendix E of the protocol).
5. Assessment of blasts in peripheral blood will be carried out at Screening, C1 D1 pre-dose, C1 onwards at D14 (or last day of dosing in each cycle; -2 d tolerance from C3 onwards), and FSV. This assessment may be performed from the Hematology sample.
6. At C1 D1, the electrocardiogram assessment will be carried out pre-dose and at 4-6 h post dose.

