7.2.2. Key definitions

Baseline values

The baseline value of an assessment is defined as the last available (non-missing) value before or on the date of first administration (Day 1) for Cycle 1.

Adverse Events (AEs)

An AE is any untoward medical occurrence in a patient (or a clinical investigation subject), receiving a medicinal product and which does not necessarily have a causal relationship with the treatment. Therefore an AE can be any unfavourable and unintended sign (including an abnormal clinically significant laboratory finding), symptom, or disease temporally associated with the use of a medicinal (investigational) product, whether or not related to the medicinal (investigational) product. All identified AEs are recorded and described on the appropriate AE page of the eCRF, except for those events occurring prior to the first dose of study medication, which are recorded on the Medical History eCRF page.

Adverse Drug Reactions (ADRs)

Untoward and unintended responses to an Investigational Medicinal Product (IMP) related to any dose administered. The definition covers also medication errors and uses outside what is foreseen in the protocol, including misuse and abuse of the product. The definition implies a 'reasonable possibility of a causal relationship between the event and the IMP. This means that there are facts (evidence) or arguments to suggest a causal relationship.

All AEs (including SAEs) have to be accurately recorded on the AE page of the patient's eCRF. Each event will be graded for severity using the classifications of NCI CTCAE v4.03. For events not addressed in the NCI CTCAE v4.03, classifications will be performed according to the following grading:

- Mild (Grade 1) - Mild; asymptomatic or mild symptoms; clinical or diagnostic observations only; intervention not indicated;
- Moderate (Grade 2) - Moderate; minimal, local or noninvasive intervention indicated; limiting age-appropriate instrumental activity of daily living;
- Severe (Grade 3) - Severe or medically significant but not immediately life-threatening; hospitalization or prolongation of hospitalization indicated; disabling; limiting self-care activity of daily living;
- Life-threatening (Grade 4) - Life-threatening consequences; urgent intervention indicated.

- Death (Grade 5) - Related to adverse event.

Serious Adverse Event (SAE) / Serious Adverse Drug Reaction (SADR)

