11.5. Safety analysis

Safety and tolerability assessments will be evaluated on the safety population by means of descriptive statistics. Summary statistics (counts / (%) | number of events) will report the incidence of AEs using combinations of these variables for the descriptive statistics stratification: CTCAE toxicity grade, relationship with study drug, seriousness, System Organ Class or Body System, Preferred Term.

AEs summary tables will be created by Cohort (dose level) and Overall.

Counts and percentages will be produced for the results of the ECG, laboratory values (clinical chemistry, haematology, coagulation, bone marrow and urinalysis), vital signs, physical examination, classified as Normal/Abnormal NCS/Abnormal CS by Cohort (dose level) and Overall, stratified by Visit and timepoint – if applicable.

For ECG and hematology, clinical chemistry, coagulation and bone marrow laboratory data, the change from baseline will be summarized for each post baseline visit with descriptive statistics by cohort. For hematology and clinical chemistry laboratory parameters shift tables will be presented with the counts of individual shifts from each of the reference range categories from baseline to the worst post-baseline value by laboratory parameter by cohort and dose level.

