11.5.4. Physical Examination

A summary table of Physical Examination parameters by Body System and Visit will be provided in the TLFs.

11.5.5. 12-ECG

A summary table of 12-Lead ECG interpretation by Visit will be provided in the TLFs. Similarly, changes from baseline for each post baseline visit will be summarised.

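### The SAP sets baseline by date only, so the Cycle 1 Day 1 ECG taken 4-6 h after the first dose becomes the reference for ECG change in Table 2.14.1

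*SAP*

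**What the plan says.** SAP 7.2.2 (Key definitions) gives one baseline rule for all assessments: "the last available (non-missing) value before or on the date of first administration (Day 1" of Cycle 1. The test is the calendar date.

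Footnote 6 to the flow chart in SAP 5.3 reads: "At C1 D1, the electrocardiogram assessment will be carried out pre-dose and at 4-6 h post dose". Footnote 6 to protocol Table 5 says the same, and the Cycle 1, Day 1 list in protocol 5.1 has "ECG (pre-dose and 4-6 h post dose".

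The general instructions in SAP 5.3 state: "On dosing days, assessments should be performed prior to SEL24/MEN1703 dosing unless specified otherwise".

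For ECG and most laboratory panels, SAP 11.5 says that "the change from baseline will be summarized for each post baseline visit with descriptive statistics by cohort". SAP 11.5.5 says "A summary table of 12-Lead ECG interpretation by Visit will be provided in the TLFs", and adds that changes from baseline are summarised in the same way. The output is Table 2.14.1 in SAP 13.2.1. None of these places gives ECG a baseline of its own.

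**The concern.** A baseline should be a record from before exposure. Here the rule admits any record from the day of first dose, and the last scheduled ECG of that day is taken on drug.

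ECG is named in the Part 2 primary endpoint (SAP 5.4.1), and Table 2.14.1 is the only table in the index that shows ECG change. The 4-6 h ECG is also the only one scheduled at a stated interval after a dose. If it serves as the reference it has no change value of its own, so the table cannot show an early effect at that time point. Later changes are measured from a value that may already contain a drug effect.

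Protocol 1.3 reports in vitro hERG inhibition (IC50 3.561 and 2.5 µM), and exclusion criterion 19 uses QTc. These are reasons to want a clean reference. They are not evidence of an effect in patients.

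**Working it through.** The plan states no figure on this point, so the check applies the rule to the schedule.

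**1. Which record the rule selects.** The inputs are the scheduled ECGs up to Day 7: Screening, C1D1 pre-dose, C1D1 4-6 h, C1D7. The SAP rule takes the latest non-missing record dated on or before the day of first dose. The alternative takes the latest non-missing record timed before the first dose.

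| Records available | SAP rule | Before-first-dose rule |
|---|---|---|
| All present | C1D1 4-6 h | C1D1 pre-dose |
| C1D1 pre-dose missing | C1D1 4-6 h | Screening |
| C1D1 4-6 h missing | C1D1 pre-dose | C1D1 pre-dose |

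So the baseline is on-drug exactly when a non-missing 4-6 h ECG exists.

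**2. Whether other text prevents this.** The instruction to assess before dosing gives way where something else is specified, and footnote 6 specifies something else for this ECG. SAP 11.5, SAP 11.5.5 and the table index are silent, and the protocol has no ECG baseline definition.

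**3. What is tabulated.** The SAP does not name the variables in Table 2.14.1. SAP 11.5 asks for descriptive statistics of change, which suggests numbers, whereas SAP 11.5.5 speaks of interpretation. Protocol 5.3.8 says "A resting 12-lead ECG will be performed at the times given in the Schedule of Study Assessment (Table 5" and lists no intervals. QTc is read as a number for eligibility ("QTc values up to 500 ms will be acceptable" in some patients, exclusion criterion 19). Numeric change is therefore plausible but not confirmed.

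**4. Effect on a numeric variable.** Let d = 4-6 h value minus pre-dose value on C1D1. Then

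later − post = (later − pre) − (post − pre) = (later − pre) − d.

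Illustration with assumed values: if d is −5, 0 or +5 ms, a later ECG with no real change from pre-dose is reported as +5, 0 or −5 ms. If the real later change is 20 ms and d is 0, 5, 10 or 20 ms, the table reports 20, 15, 10 or 0 ms.

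**5. Effect on interpretation categories.** Assumed example: pre-dose Normal, 4-6 h Abnormal NCS, C2D1 Normal. The table shows a move from Abnormal NCS to Normal, although nothing has changed from pre-dose.

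**6. Later visits.** Four ECG visit types follow C1D1: C1D7, C2D1, Day 1 of Cycle 3 onwards, and the final visit. C1D7 falls within dosing. The two Day 1 types (2 of 4) are pre-dose by default. With the last dose on Day 14 and the next cycle starting on Day 22, the gap is 22 − 14 = 8 days, or 6 to 10 with the ±2-day window. These visits compare an off-dosing record with an on-drug one. The final visit is planned 7-30 days after the last dose (footnote 17), but protocol 3.6 lets an unscheduled assessment replace it, so its timing can vary.

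**7. Reach.** Six change-from-baseline tables are indexed: 2.6.1, 2.7.1, 2.8.1, 2.9.1, 2.11.1 and 2.14.1. One of the six is affected. For patients, Part 1 treated 2+3+3+3+3+7+3+1 = 25, and the all-comers cohort adds 23, giving 48 dosed before Version 12. With about 20 IDH-mutant patients the total is about 68, and 48/68 = 71%. Only the Version 12 schedule is visible, and it governs the IDH-mutant cohort.

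**The case against.** The strongest objection is that the documents show a rule, not a program. A date-only rule does not itself order two records on the same date, and a programmer could use the record time or a pre-dose label. On that view the SAP is ambiguous rather than wrong. This stands only as far as actual programming is concerned: nobody can tell from the documents how the flag is derived. But *last* most naturally means the later record, and choosing the pre-dose ECG would be an undocumented departure from the SAP text.

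A second objection is that no ECG data are lost. SAP 11.5 stratifies the Normal/Abnormal counts by visit and, where applicable, time point. Table 2.14 and Listing 4.17 do not depend on baseline either. This is correct, and it limits the point to Table 2.14.1.

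Third, change is summarised by visit, so even a pre-dose baseline would not guarantee a row for the 4-6 h ECG. That is fair: the row has to be requested separately.

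Fourth, protocol 5.3.8 does not require the clock time of the ECG to be recorded, unlike the sections on vital signs and laboratory samples. The time-point stratification in SAP 11.5 suggests that a pre-dose/4-6 h label is captured, but does not prove it.

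Finally, the size of any distortion is unknown. The documents give no human ECG effect, and the dog safety study in protocol 1.3 found none on lead II intervals. This also stands.

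**Conclusion.** The concern holds. Followed as written, SAP 7.2.2 makes an on-drug ECG the baseline for every patient with a non-missing 4-6 h record, and nothing else in the SAP or protocol corrects it. This conclusion rests on the text and does not depend on which ECG variables are tabulated.

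The severity is minor. One descriptive table is affected, safety analysis is descriptive throughout, and no decision rule uses ECG change. For numeric variables the error is minus d for each patient, with d unknown in sign and size and possibly zero. The number of patients affected cannot be fixed: it is 0 to about 20 on the visible schedule, and up to about 68 only on the assumption that every earlier protocol version had the same two C1D1 ECGs.

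**What to change.** In SAP 7.2.2, define baseline as the most recent non-missing value obtained before the date and time of first SEL24/MEN1703 intake. Where no clock time exists, use the scheduled time-point label (pre-dose or 4-6 h). For ECG this gives the C1D1 pre-dose record, or Screening if that is missing.

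In SAP 11.5.5, state that the C1D1 4-6 h ECG is a post-baseline time point in Table 2.14.1, and name the variables the table reports.

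The cost is one sentence on baseline, one baseline flag in the analysis dataset and one extra table row, plus the list of variables. No new data are needed, provided that the ECG time or the time-point label is in the database. That should be confirmed first.

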7.3. Analysis populations

The following analysis populations will be considered in the statistical analysis:

- **Safety population:** the safety set consists of all patients that have received at least one dose of SEL24/MEN1703.
- **DD population:** the dose determining set will consist of all patients in each cohort that have completed one cycle of treatment and patients that discontinued earlier due to a DLT occurring in this period. This population will be used for the dose escalation Part 1.
- **PK population:** all patients who received any dose of SEL24/MEN1703 and have sufficient data for PK analysis. Therefore, all subjects receiving study drug and having at least 1 measurable drug concentration will be included in the PK population. If there are subjects who do not have sufficient samples for the PK non-compartmental analysis (NCA), a modified NCA will be conducted in which some or all PK parameters may not be estimated for those subjects, but available PK concentrations will still be tabulated and graphed.

For some objectives (e.g. anti-leukemic or PD activity), a subgroup of patients of the safety set with respective baseline and post-baseline measurements will be used along with the safety population.

- **Efficacy population:** the efficacy set will consist of all patients in each cohort that have completed one cycle of treatment (considering both the treatment and the washout period - 21 days) and have taken at least 75% of the study drug during the first cycle.

Thus, anti-leukemic activity will be analyzed on both the safety and the efficacy population.

Patients who were screened but did not receive any treatment will be listed and will not be part of any summary table.

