### 3.3. Definition of Evaluable Patient and Replacement of Patients

In Part 1 Cycle 1, a patient must have received at least 12 of their 14 doses of SEL24/MEN1703 within the required 14-day treatment period in order to be evaluable. If a patient is withdrawn from the study for reasons other than a DLT-associated event before the end of the first treatment cycle, the patient must be replaced so that the required number of patients in the cohort is evaluable for the dose escalation decision. Patients who withdraw from the study or discontinue treatment after completion of the first treatment cycle will not be replaced.

In Part 2, patients may be replaced if they are not considered evaluable for safety (all patients who received at least a dose of SEL24/MEN1703). Patients in Part 2 may also be replaced if they received one or more administrations of SEL24/MEN1703 without having one post-treatment bone marrow disease assessment.

In this latter event, patients may be replaced only if the hematology assessments performed on peripheral blood shall not indicate a clear disease progression.

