### 8.2. Populations

Two populations for analysis are considered:

The dose determining set will consist of all patients in each cohort that have completed one cycle of treatment and patients that discontinued earlier due to a DLT occurring in this period. This population will be used for the dose escalation Part 1.

For all other objectives, the safety set consisting of all patients that have received at least one dose of SEL24/MEN1703 will be used. Patients will be also be categorized by cohort and by dose level received.

For some objectives (e.g. anti-leukemic or PD activity), a subgroup of patients of the safety set with respective baseline and post-baseline measurements will be used.

Patients who were screened but did not receive any treatment will be listed and will not be part of any summary table.

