3.1. Changes from study protocol

All analyses detailed in this document are as specified in the protocol and subsequent amendments, no major changes from the protocol-planned primary analysis have been performed.

4. Study overview

MEN1703 is a dual kinase inhibitor targeting PIM (PIM1, PIM2, PIM3) and FLT3 kinases which will be supplied as formulated drug product in a gelatin capsule.

This trial was designed as a Phase I/II, open-label, multi-center, dose escalation study to estimate the MTD (or MAD) of SEL24/MEN1703 in patients with AML. At the end of Part 1 a RD of SEL24/MEN1703 was selected for further evaluation in Part 2. In Part 2 the safety and anti-leukemic activity of SEL24/MEN1703 was further assessed in the study population. The starting dose was 25 mg SEL24/MEN1703 taken orally QD for 14 consecutive days over a 21-day treatment cycle.

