12.1. Efficacy analysis

The Overall Survival (OS) is calculated as:

- In case of all-cause death:
 $OS = date\ of\ death - date\ of\ first\ study\ drug\ administration + 1;$
- In case of censored information not for drop-out:
 $OS = date\ of\ end\ of\ observation\ period\ (i.e.\ study\ end / end\ of\ survival\ follow-up) - date\ of\ first\ study\ drug\ administration + 1;$
- In case of censored information for drop-out:
 $OS = last\ date\ known\ alive - date\ of\ first\ study\ drug\ administration + 1.$

The Relapse Free Survival (RFS) is calculated as:

- In case of relapse or all-cause death:
 $RFS = date\ of\ relapse\ or\ death\ (whichever\ comes\ first) - date\ of\ first\ CR,\ CRi,\ CRh\ or\ CR_{MRD-} + 1;$
- In case of censored information:
 $RFS = date\ of\ last\ relapse-free\ disease\ assessment - date\ of\ first\ CR,\ CRi,\ CRh\ or\ CR_{MRD-} + 1.$

The Event Free Survival (EFS) is calculated as:

- In case of relapse, treatment failure or all-cause death:
 $EFS = date\ of\ relapse,\ disease\ progression,\ treatment\ failure\ (failure\ to\ achieve\ CR/CRh/CRi/CR_{MRD-}\ after\ at\ least\ five\ cycles\ of\ treatment)\ or\ death\ (whichever\ comes\ first) - date\ of\ first\ study\ drug\ administration + 1;$
- In case of censored information:
 $EFS = date\ of\ last\ relapse-free/treatment-failure-free/progression-free\ disease\ assessment - date\ of\ first\ study\ drug\ administration + 1.$

The Duration of Response (DoR) is calculated as:

- In case of relapse, progressive disease or death due to progressive disease:
 $DoR = date\ of\ relapse\ of\ any\ type/progressive\ disease/death\ due\ to\ progressive\ disease - date\ of\ first\ CR,\ CRi,\ CRh,\ CR_{MRD-},\ MLFS\ or\ PR + 1;$
- In case of censored information:
 $DoR = date\ of\ last\ relapse-free\ disease\ assessment - date\ of\ first\ CR,\ CRi,\ CRh,\ CR_{MRD-},\ MLFS\ or\ PR + 1.$

No formal statistical analysis will be performed on anti-leukemic parameters.

Anti-leukemic activity data will be collected throughout Part 1 and Part 2 and will be summarized by cohort, by dose and overall.

Measures of anti-leukemic activity will be computed on both safety and efficacy populations and they will include:

- Changes (absolute and %) in pre- and post-treatment levels of leukemic blasts in the peripheral blood and/or bone marrow;
- Number and percentages of patients who reported as best overall response one of the following: CRM RD-, CR, CRh, CRi, MLFS, PR, SD, PD;
- Duration of response (DoR);

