Efficacy Tables (to be performed on both efficacy population as well as safety population)

Table 3.1: Summary of Tumor Response by Visit
 Table 3.2: Summary of Tumor Response Endpoints
 Table 3.3: Summary of Time to Event Endpoints

PK Tables

Table 4.1: Summary statistics of MEN1703 PK concentration in plasma by cohort, cycle, day, IDH mutational status and nominal time point, and by dose, cycle, day, IDH mutational status and nominal time point
 Table 4.2: Summary statistics of MEN1703 PK parameters by cohort, cycle, day, IDH mutational status and nominal time point, and by dose, cycle, day, IDH mutational status and nominal time point.
 Table 4.3: Summary statistics of MEN1703 PK concentration in urine by cohort, cycle, day, IDH mutational status and nominal time point, and by dose, cycle, day, IDH mutational status and nominal time point
 Table 4.4: Summary statistics of MEN1703 urinary PK parameters by cohort, cycle, day, IDH mutational status and nominal time point, and by dose, cycle, day, IDH mutational status and nominal time point
 Table 4.5: Summary statistics of MET3 PK concentration in plasma by cohort, cycle, day, IDH mutational status and nominal time point, and by dose, cycle, day, IDH mutational status and nominal time point
 Table 4.6: Summary statistics of MET3 PK parameters by cohort, cycle, day, IDH mutational status and nominal time point, and by dose, cycle, day, IDH mutational status and nominal time point.

Table 4.7: Summary statistics of MET3 PK concentration in urine by cohort, cycle, day, IDH mutational status and nominal time point, and by dose, cycle, day, IDH mutational status and nominal time point

Table 4.8: Summary statistics of MET3 urinary PK parameters by cohort, cycle, day, IDH mutational status and nominal time point, and by dose, cycle, day, IDH mutational status and nominal time point

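### SAP 7.3 adds an efficacy population conditioned on completing Cycle 1; it is not in the protocol, is not declared as a change, and no lead set is named for response

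*SAP*

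**What the plan says.** Protocol 8.2 names two populations: the dose determining set and the safety set. For some objectives, with anti-leukemic activity given as an example, it adds that "a subgroup of patients of the safety set with respective baseline and post-baseline measurements will be used". It has no efficacy population.

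SAP 7.3 keeps that idea in slightly changed form: the subgroup "with respective baseline and post-baseline measurements will be used along with the safety population". It then defines an efficacy population of patients who "completed one cycle of treatment (considering both the treatment and the washout period - 21 days) and have taken at least 75% of the study drug" in the first cycle, and concludes: "Thus, anti-leukemic activity will be analyzed on both the safety and the efficacy population". SAP 12.1 repeats this: "Measures of anti-leukemic activity will be computed on both safety and efficacy populations". The table index in SAP 13.2.1 plans Tables 3.1 to 3.3 on both sets.

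The disposition list in SAP 11.4 counts the dose determining, safety and efficacy populations. The measured subgroup has no disposition row there and no table of its own in SAP 13.2.1. No section says which set leads for response.

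SAP 3.1 opens: "All analyses detailed in this document are as specified in the protocol and subsequent amendments". It adds that the protocol-planned primary analysis has not changed in any major way.

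**The concern.** Entry to the efficacy population is decided after treatment starts, by things that treatment and disease affect: being alive at day 21, still being on study, and having tolerated enough drug. A patient who dies, progresses and stops, or stops for toxicity in Cycle 1 leaves the denominator. Such patients are mostly non-responders. The SAP's own dose determining set avoids this by keeping patients who stopped early because of a DLT. The efficacy set has no such provision.

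This is an open-label, single-arm study, so the descriptive response rate is the evidence of activity. With two denominators, no lead and no declaration of the change, the choice of headline rate can be made after the data are seen. A reader relying on SAP 3.1 would not know that one of the two sets is absent from the protocol.

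**Working it through.** **Plan's own count.** The cohorts in SAP Table 1 sum to 2+3+3+3+3+7+3+1 = 25. Adding the two planned Part 2 cohorts gives 25+20+20 = 65, the figure in SAP section 8. The all-comers cohort treated 20+3 = 23. These totals reproduce but do not settle the point; they supply N = 20 and N = 23.

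**Dose threshold.** 75% of 14 doses is 10.5, so at least 11 doses are needed (11/14 = 78.6%). Protocol 3.3 says that in Part 1 Cycle 1 "a patient must have received at least 12 of their 14 doses of SEL24/MEN1703" to be evaluable, which is 12/14 = 85.7%. The SAP threshold is therefore not the protocol's evaluability rule carried over.

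**Membership against the protocol subgroup.** It differs in both directions.
- Peripheral blasts are scheduled at Cycle 1 Day 14 (Protocol Table 5, footnote 5). A patient with that count who dies or stops before day 21 can be in the protocol subgroup but not in the efficacy set.
- The first scheduled post-baseline marrow is C3 D1, nominally day 43, unless blood results suggest a response earlier (footnote 7). A patient with 11 doses, 21 completed days and no later marrow is in the efficacy set but has no marrow-based response measurement.

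**Size against the safety population.** Let N be dosed patients, r responders and k patients excluded by the rule. If every excluded patient is a non-responder, the rate moves from r/N to r/(N-k), a factor of N/(N-k). The documents give neither r nor k; both are assumed.

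| N | k | Factor | Assumed r | Safety set | Efficacy set |
|---|---|---|---|---|---|
| 20 | 2 | 1.11 | 4 | 20.0% | 22.2% |
| 20 | 4 | 1.25 | 4 | 20.0% | 25.0% |
| 20 | 6 | 1.43 | 4 | 20.0% | 28.6% |
| 23 | 2 | 1.10 | 3 | 13.0% | 14.3% |
| 23 | 4 | 1.21 | 3 | 13.0% | 15.8% |
| 23 | 6 | 1.35 | 3 | 13.0% | 17.6% |

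For r from 2 to 5 and k from 2 to 6, across both N, the absolute rise runs from 0.8 to 10.7 percentage points. Exact 95% intervals are wide: 3/23 is 13.0% (2.8 to 33.6) and 3/19 is 15.8% (3.4 to 39.6).

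The rise is usual, not certain. If one of two excluded patients had responded, 3/23 = 13.0% would become 2/21 = 9.5%.

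**What the documents say about k.** Part 1 had 1+1+2+1 = 5 patients with a DLT and 2 who were not DLT evaluable. If evaluability followed Protocol 3.3, at most 7 of 25 could fail the rule, a factor of at most 25/18 = 1.39. The documents do not say how many of the 7 would fail it. Part 2 has no comparable figure.

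**Size against the protocol subgroup.** Take r = 3 and N = 23, with both exclusion counts assumed.
- Subgroup missing 2, efficacy set missing 4: 3/21 = 14.3% against 3/19 = 15.8%.
- Subgroup missing 6, efficacy set missing 3: 3/17 = 17.6% against 3/20 = 15.0%.

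The sign changes with the counts.

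**The case against.** The strongest reply is that nothing has been lost. The SAP keeps the protocol's subgroup sentence and plans every efficacy table on the safety population as well, so early failures remain in a reported analysis. That stands. A reader might infer that the SAP replaces the protocol's activity set; the text does not support this. What can be said is that the subgroup survives in one sentence with no table or disposition row.

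A reader might also infer that the efficacy set inflates response relative to the protocol's definition. That is not supported either. The protocol subgroup also drops early failures who have no post-baseline measurement. Response needs marrow under Appendix D, so a marrow-based subgroup can be stricter than a 21-day rule. Upward movement is expected only against the safety population.

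Third, activity is a secondary objective, summarised descriptively, with no test or threshold to pass. That is correct: no error rate is affected, and the primary DLT and safety analyses are untouched.

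Fourth, Protocol 8.4 leaves detail to the SAP and anticipates populations defined there, and Protocol 3.6 refers to subjects evaluable for efficacy without defining them. So the SAP was entitled to define a set. This does not answer the disclosure point: the opening clause of SAP 3.1 covers all analyses, and its reassurance about the primary analysis does not cover a secondary population.

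**Conclusion.** The point holds in limited form. SAP 7.3 adds an outcome-conditioned efficacy population that Protocol 8.2 does not contain and SAP 3.1 does not declare. It is reported beside the safety population with no lead named.

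Against the safety population the response rate will usually be higher, by N/(N-k) when all excluded patients are non-responders. With N=20 that is 1.11 for k=2 and 1.25 for k=4. These factors rest on assumed k and on all dosed patients forming the safety-set denominator. The shift is small beside the sampling uncertainty, but it is systematic and can be avoided. No direction can be claimed against the protocol's own subgroup.

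**What to change.** Make four changes to the SAP before database lock.

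- In 7.3 and 12.1, name the safety population as the lead set for ORR, PR rate and HSCT rate, and count an undocumented response as non-response. The second part needs an explicit line because SAP 11.3 applies an observed-cases approach throughout.
- Label the 75%/21-day set supportive, and list each excluded patient with the reason.
- Give the protocol's baseline-plus-post-baseline subgroup a defined use consistent with Protocol 8.2, such as change in blasts, with a disposition row and a table. Otherwise declare its removal.
- Record the added population in SAP 3.1 as a change from the protocol.

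Both sets of efficacy tables are already planned, so the cost is mainly wording, plus an exclusion listing and a table for the subgroup if it is kept. The downside is a slightly less favourable headline rate. For illustration, with 3 assumed responders among 23 dosed and 4 non-responders excluded, the lead figure would be 13.0%, with 15.8% shown as supportive.
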